7.4 The Use of Oseltamivir as Standard of Care

All subjects will receive oseltamivir 75 mg BID for 5 days as part of SOC. Treatment with oseltamivir may be extended for up to 5 additional days (up to 20 doses of total therapy) if clinical symptoms warrant further treatment as assessed by the Investigator. Oseltamivir (Tamiflu) will be provided by the Sponsor. Note: based on SOC, subjects may have started oseltamivir therapy prior to randomization.

For patients unable to swallow, oseltamivir capsules can be opened and mixed with liquid for ease of administration.

Dose adjustment is recommended for patients with a serum creatinine clearance of 60 mL/min or less⁹ (see Table 7).

Table 7. Recommended Dosage Modifications for Treatment of Influenza in Adults with Renal Impairment or End-Stage Renal Disease on Dialysis^a

Renal Impairment (Creatinine Clearance)	Recommended Treatment Regimen^b
Mild (> 60-90 mL/minute)	75 mg BID for 5 days
Moderate (> 30-60 mL/minute)	30 mg BID for 5 days
Severe (> 10-30 mL/minute)	30 mg once daily for 5 days
ESRD patients on hemodialysis	30 mg immediately and then 30 mg after every hemodialysis cycle (treatment duration not to exceed 5 days)
ESRD patients on continuous ambulatory peritoneal dialysis ^c (≤ 10 mL/minute)	A single 30-mg dose administered immediately
ESRD patients not on dialysis	Tamiflu is not recommended

ESRD = end-stage renal disease.

^a Creatinine clearance to be calculated using Cockcroft-Gault formula.

^b Capsules or oral suspension can be used for 30-mg dosing.

^c Data derived from studies in continuous ambulatory peritoneal dialysis patients.

For patients with renal insufficiency, refer to prescribing information for administration of oseltamivir.⁹

The dose of oseltamivir (75 mg BID for 5 days) was chosen for this study based on the approved dose in the United States and other regions for the treatment of uncomplicated influenza infection. The dosage regimen of oseltamivir as the SOC in this study serves as a clinically appropriate, ethically acceptable treatment.

7.5 Pretreatment Regimen

All subjects will be given a pretreatment regimen of PO or IV diphenhydramine 50 mg plus either ibuprofen 400 mg or acetylsalicylic acid 320-325 mg PO or crushed and given through the nasogastric tube approximately 60 minutes before IV infusion of VIS410/placebo.

If the subject has any history of delayed gastric emptying, including premenstruation syndrome or menstruation, the subject may receive premedications 120 minutes prior to IV infusion of VIS410/placebo.

Refer to the Pharmacy Manual for directions on storage, handling, stability data, and preparation and use of diphenhydramine, ibuprofen, and acetylsalicylic acid.

For more information, refer to the prescribing information for ibuprofen¹⁰ and acetylsalicylic acid.¹¹

7.6 Other Medications Administered in This Study

All prescription and over-the-counter medications that the subject received from 7 days prior to study drug and throughout the study (up to the LFU evaluation) will be documented in the EDC.

Herbal, nutritional, and dietary supplements received by the subject within 7 days before randomization will be documented in the EDC only if medically indicated.

Administration of concomitant medications must be reported in the appropriate section of the EDC along with dates of administration and reasons for use. Generic names for medications should be used, if possible.

Refer to the Pharmacy Manual for directions on storage, handling, stability data, and preparation and use of oseltamivir.

For more information, refer to the prescribing information for oseltamivir.⁹

7.7 Treatment Compliance

Investigative product will be administered by study staff, and all drug administration data will be reported in the EDC and the medical records of each subject.

The number of oseltamivir doses administered while the subject is in the hospital will be documented by the Investigator or his/her designee. In case of discharge while on oseltamivir therapy, subjects will document the number of doses taken at home and any missed doses; subjects self-administering oseltamivir at home will bring the pack(s) to each study visit so study staff may count and record the number of pills taken. Any unused capsules must be returned to the study site.

7.8 Storage and Drug Accountability

The Investigator (or designee) is responsible for the safe storage of all study drugs assigned to the clinical site. The investigational product should be stored in a locked, secure storage facility with access limited to those individuals authorized to dispense the investigational product, and maintained within the appropriate ranges of temperature. All study drugs must be stored in the original packaging and as specified at delivery.

The study investigational product be stored between 2°C and 8°C and should be protected from light during storage at the clinical site.

For storage of oseltamivir (Tamiflu), diphenhydramine, ibuprofen, and acetylsalicylic acid, refer to the manufacturer's prescribing information. Also refer to the Pharmacy Manual for directions on storage, handling, stability data, and preparation and use of diphenhydramine, ibuprofen, and acetylsalicylic acid.

Regular temperature recordings of the study drug storage room at the clinical site should be performed. In case a deviation in the storage conditions should occur, the site must not further dispense the affected study drug; instead, the Sponsor should be notified and will confirm whether or not the study drug may be further dispensed.

The Investigator is responsible for ensuring that all study drugs received at the clinical site are inventoried and accounted for throughout the study.

Study drugs should be dispensed under the supervision of the Investigator, a qualified member of the investigational staff, or by a hospital/clinic pharmacist. The Investigator must maintain accurate records demonstrating date and amount of drugs administered to whom and by whom. Study drugs will be supplied only to subjects participating in the study.

The monitor responsible for drug accountability will periodically check the supplies of study drugs held by the Investigator or pharmacist to ensure accountability and appropriate storage conditions for all the study drugs held at the site.

Unused study drugs must be available for verification by the Sponsor's monitor responsible for drug accountability during on-site monitoring visits. Any discrepancies between returned and expected returned study drugs should be explained.

After the last visit of the last subject in the study (LSLV), any used and unused investigational product will be returned to the Sponsor or, with the Sponsor's written permission, destroyed at the investigative site per the standard operating procedures.

Hazardous materials, such as used needles and syringes, should be disposed of immediately in a safe manner and therefore will not be retained for drug accountability purposes.

8.0 STUDY METHODS AND PROCEDURES

Table 1 summarizes the schedule for study visits and procedures performed at each study visit.

8.1 Prior & Concomitant Therapy

All medications taken within 7 days prior to signing of the informed consent form will be documented in the EDC. All therapies other than the study drug administered from signing the informed consent form until the last study visit must be recorded in the EDC system (name of the drug, dosage, route, and dates of administration).

8.1.1 Permitted Prior Therapy

Subjects are allowed to receive up to 6 doses of an approved anti-influenza therapy within the prior 96 hours (ie, oral oseltamivir, inhaled zanamivir, or oral ribavirin) between onset of symptoms and VIS410/placebo dosing.

8.1.2 Permitted Concomitant Therapies

Use of contraception or other concomitant therapy for management of subjects' other underlying medical conditions is permissible during the study.

All other concomitant medications necessary for the health and well-being of the subject will be permitted. In addition, any other treatment (not explicitly excluded) which is considered necessary for the subject's welfare may be given at the discretion of the Investigator.

8.2 Prohibited Prior & Concomitant Medications

8.2.1 Prohibited Prior Medications

Per Exclusion Criterion 2 (Section 5.2.2), subjects are not allowed to receive monoclonal antibody products within 3 months prior to VIS410/placebo dosing.

Per Exclusion Criterion 3 (Section 5.2.2), subjects who have taken more than 6 doses of an approved anti-influenza therapy within the prior 96 hours (ie, oral oseltamivir [Tamiflu], inhaled zanamivir [Relenza], or oral ribavirin) between onset of symptoms and VIS410/placebo dosing will be excluded from the study.

8.2.2 Prohibited Concomitant Medications

Per Exclusion Criterion 2 (Section 5.2.2), subjects will not be allowed to receive additional monoclonal antibody products during the study period. Following randomization, use of other antiviral therapy for treatment of influenza A infection will not be permitted. Excluded antiviral medications include but are not limited to rimantadine, amantadine, peramivir, zanamivir, and laninamivir.

The use of symptom-modifying drugs, such as NSAIDs, antihistamines, or pseudoephedrine, are not specifically excluded; however, their use outside of pretreatment should be discouraged by the Investigator, and paracetamol/acetaminophen should be encouraged as a replacement medication.

8.3 Schedule of Examination Procedures by Study Visit

The study comprises up to 8 study visits over approximately 8 weeks. Subjects will attend the clinic at every study visit.

AEs will be recorded from dosing to the subject's last visit.

Table 1 summarizes the schedule for study visits and procedures performed at each study visit.

8.3.1 Sequence of Assessments at a Single Visit

If the following assessments are to be performed at the same study visit, the FluPRO Questionnaire should be completed first, when possible:

- FluPRO Questionnaire
- ECG
- Blood sampling
- Nasopharyngeal swab

8.3.2 Day of Treatment Procedures (Day 1)

On Day 1, eligibility of the subjects will be confirmed and assessments will be performed as described in Table 1.

All results from the screening procedures required to evaluate eligibility must be available prior to randomization on Day 1. Any abnormal assessment at the screening will be assessed according to its clinical relevance, and if found relevant, the subject will not be included in the study.

Once a subject has fulfilled the entry criteria, he/she will be assigned a unique identifier. The site's unblinded pharmacist or properly trained designee will randomize the subject using the IWRS.

On Day 1, all subjects will receive the pretreatment regimen prior to receiving VIS410/placebo.

8.3.3 Post-Treatment Procedures (Day 3 to 56)

Subjects will be monitored daily while in the hospital (up to Day 14) with an additional visit on Day 28 (± 3 days), and the last follow-up visit on Day 56 (± 7 days) per the procedures and

schedule listed in Table 1. Note: subjects discharged from the hospital prior to Day 14 will attend the applicable outpatient follow-up visit(s) (eg, Day 3, Day 5, Day 7, Day 14) per Table 1.

In order to provide some flexibility for the subjects regarding the site visits and to maintain the integrity of the study design, a time window is permitted for the follow-up visits in case of time conflict or unforeseen circumstances.

8.4 Subject Diary

A subject diary will be provided upon discharge from the hospital and will record the following:

- Daily oseltamivir dosing to be completed for as long as the subject continues to take oseltamivir
- Daily VAS for assessing resumption of usual activities to be completed up until either the subject reports that all pre-influenza usual activities can be performed or Day 56, whichever comes first
- Daily Influenza Patient Reported Outcomes (FluPRO) Questionnaire to be completed until Day 14, if applicable

9.0 ADVERSE EVENTS

9.1 Definitions

9.1.1 Adverse Event

An AE is any untoward medical occurrence in a patient administered a medicinal (investigational or non-investigational) product in a clinical study. An AE does not necessarily have a causal relationship with the treatment. An AE can therefore be any unfavorable and unintended sign (including an abnormal finding), symptom, or disease temporally associated with the use of a medicinal (investigational or non-investigational) product, whether or not related to that medicinal (investigational or non-investigational) product.

This includes any occurrence that is new in onset or aggravated in severity or frequency from the baseline condition, or abnormal results of diagnostic procedures, including clinical laboratory test abnormalities.

9.1.2 Signs and Symptoms of Influenza vs Adverse Events

The solicited and unsolicited signs and symptoms of influenza will not be reported as AEs as these constitute an endpoint of the study and will be recorded as such.

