Eligible subjects will be randomized to receive either oseltamivir + VIS410 2000 mg, oseltamivir + VIS410 4000 mg, or oseltamivir + placebo (0.9% sodium chloride) at a ratio of 1:1:1 using a permuted block randomization method according to the table below:

Sample Size	Treatment	VIS410 Dose ^a	Oseltamivir Dose ^b	Infusion
n = 40	VIS410 + oseltamivir	2000 mg IV	75 mg administered BID	Infused over
n = 40	VIS410 + oseltamivir	4000 mg IV	for a minimum of 5 days	120 minutes
n = 40	Placebo ^c + oseltamivir	0 mg IV		

^a Dose administered in 200 mL

^b Dosage and administration should follow local prescribing information for oseltamivir based on renal function.

^c 0.9% sodium chloride (200 mL).

Oseltamivir (Tamiflu[®]) will be provided by the Sponsor. Treatment with oseltamivir may be extended for up to 5 additional days (up to 20 doses of total therapy) if clinical symptoms warrant further treatment as assessed by the Investigator. Note: based on SOC, subjects may have started oseltamivir therapy prior to randomization.

Study assessments are outlined in Table 1. Subjects discharged from the hospital prior to Day 14 will attend the applicable outpatient follow-up visit(s) (eg, Day 3, Day 5, Day 7, Day 14) per Table 1.

An independent data safety monitoring board (DSMB) will be established to review all available safety data after 30 subjects and again after approximately 70 subjects have completed Day 14 assessments. The assessment of safety will be determined from vital sign measurements, physical examinations, hematology, chemistry and urinalysis laboratory testing, 12-lead electrocardiograms (ECGs), use of concomitant medications, and review of adverse events (AEs). Based on the safety data provided, the DSMB will determine if it is acceptable to continue the study or reduce the dose as appropriate. Dosing will temporarily pause while the DSMB meets if there are 4 treatment-related serious adverse events (SAEs) or 4 severe gastrointestinal (GI) treatment-emergent adverse events (TEAEs) that require intervention, which is defined as requiring IV fluid and medication to decrease the frequency of diarrhea (ie, loperamide).

Additional DSMB reviews can occur throughout the trial as deemed necessary by the DSMB or Sponsor to ensure subject safety and well-being. Study enrollment and dosing will continue while the DSMB evaluates data.

Study Population

Number of Subjects

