5.2.1 Inclusion Criteria

Subjects meeting all of the following criteria are eligible to participate in this study:

1. Male and female subjects aged ≥ 18 years. For a country where the legal age of consent is >18 years old, the country requirements should be followed.
2. Test positive for influenza A by rapid antigen test or with another commercially available test on an adequate nasopharyngeal specimen in accordance with the manufacturer's instructions, or an acceptable local test including, PCR, FIA, or ELISA.
3. Onset of influenza symptoms no more than 5 days before VIS410/placebo infusion; symptoms may include cough, dyspnea, sore throat, fever, myalgias, headache, nasal symptoms (rhinorrhea, congestion), fatigue, diarrhea, anorexia, nausea, and vomiting.
4. Requirement for oxygen support including any positive pressure ventilation (PPV).
5. Women of childbearing potential must have a negative pregnancy test within 2 days prior to VIS410/placebo infusion.
6. Women should fulfill one of the following criteria:
 - a. Post-menopausal: either amenorrhea ≥ 12 months or follicle stimulating hormone > 40 mIU/mL as documented in their medical history
 - b. Surgically sterile; hysterectomy, bilateral oophorectomy, or tubal ligation
 - c. Women of childbearing potential participating in heterosexual relations must be willing to use adequate contraception from screening until 60 days post-VIS410/placebo infusion (see Section 6.2).
7. Non-vasectomized (or vasectomized less than 6 months prior to dosing) male subjects who have a female partner of childbearing potential must use an effective birth control method (see Section 6.2) when having heterosexual intercourse, from screening until 60 days post-VIS410/placebo infusion.
8. Subject is able and willing to comply with study procedures, as per protocol.
9. Subject, or a legally acceptable representative, is able to understand the purpose and risks of the study and willing to give voluntary written informed consent.

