6.3.6 Signs and Symptoms of Influenza

The Influenza Patient-Reported Outcome (FluPRO) Questionnaire (see 14.1) must be completed (ie, self-reported) by the subject at baseline (Day 1) and post-dose as defined in Table 1. Each subject will be evaluated at baseline to determine if subject is able to independently report his/her influenza signs and symptoms. Subjects who are not able to complete the baseline FluPRO Questionnaire are exempt from this assessment throughout the study. The subject's inability to self-report his/her symptoms of influenza at baseline should be documented in the EDC.

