9.1.3 Adverse Event of Special Interest

An adverse event of special interest (AESI; serious or non-serious) is one of scientific and medical concern specific to the Sponsor's product or program, for which ongoing monitoring by the Sponsor may be warranted. Such an event should be entered into EDC in a timely manner and if applicable, reported as an SAE. Depending on the nature of the event, rapid communication by the trial Sponsor to other parties (eg, regulators) might also be warranted (based on CIOMS VI).

For VIS410, the AESIs include the following:

- Abdominal cramping
- Diarrhea/Loose stool
- Nausea
- Vomiting
- Pruritus
- Rash
- Hypotension
- Throat tightening
- Trouble breathing or wheezing

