10.7.1 Adverse Events

The original terms in the electronic data capture (EDC) system used by Investigators to identify AEs other than symptoms of influenza A will be fully described and coded according to the Medical Dictionary for Regulatory Activities (MedDRA). The reported AEs will be allocated to phases based on their start date. All AEs will be listed. All AEs with onset during the treatment phase (ie, treatment-emergent AEs [TEAEs]) will be summarized.

AEs will be summarized overall and by treatment group and by MedDRA body organ system and preferred term, severity, relatedness, and seriousness.

The difference in proportions of subjects with AEs, TEAEs, hypersensitivity reaction, anaphylactic reaction, AESIs, and SAEs between treatment groups will be calculated.

Special attention will be paid to those subjects who died, discontinued due to an AE, or experienced a severe or serious AE. Summaries, listings, and narratives will be provided, as appropriate.

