Sneezing					
Coughing					
Coughed up mucus or phlegm					

	0 times	1 time	2 times	3 times	4 or more times
How many times did you vomit?					
How many times did you have diarrhea?					

August 20, 2015 FluPRO Version 2.0

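### Protocol 9.1.2 keeps influenza symptoms out of adverse event reporting, 9.1.1 and 9.1.3 call for many of the same GI and breathing events to be recorded, and nothing says which rule prevails

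*Protocol*

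**What the plan says.** Protocol 9.1.2: "The solicited and unsolicited signs and symptoms of influenza will not be reported as AEs as these constitute an endpoint of the study". It makes no exception for new onset, worsening, timing after the infusion or AESI terms. Protocol 10.7.1 and the synopsis carry the exclusion into the analysis: "AEs other than symptoms of influenza A will be fully described and coded".

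Two neighbouring sections point the other way. Section 9.1.1 treats a new occurrence, or one worse than at baseline, as an AE. Section 9.1.3 lists nine AESI terms, including "Diarrhea/Loose stool", and tells sites to enter such events in EDC whether or not they are serious.

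The protocol also defines the same events as influenza symptoms. Inclusion criterion 3 (5.2.1) names dyspnea and, at the end of its list, "fatigue, diarrhea, anorexia, nausea, and vomiting". FluPRO (14.1) solicits trouble breathing, nausea, stomach ache and vomiting, and asks "How many times did you have diarrhea".

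Three outputs depend on what is recorded as an AE: the primary safety endpoint (3.1.2), the AESI summaries (SAP 12.1, which identifies AESIs by an eCRF event-type field), and the trigger of "4 severe gastrointestinal (GI) treatment-emergent adverse events (TEAEs) that require intervention" (synopsis; Protocol 11.4).

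**The concern.** GI events are the main known toxicity of VIS410 (Protocol 1.5.1.1), and patients hospitalized with influenza can have the same complaints from the disease. New diarrhea some hours after the infusion fits both 9.1.2, which says not to report it as an AE, and 9.1.3, which says to enter it as an AESI. With approximately 140 planned sites, different answers are likely. An event kept out under 9.1.2 cannot be recovered at analysis.

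The trial is meant to describe the tolerability of two dose levels and to inform Phase 3. Under-recording of drug-related GI events would make VIS410 look better tolerated than it is and blur the comparison of 2000 mg with 4000 mg.

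**Working it through.** **1. Overlap.** The AESI list in 9.1.3 against inclusion criterion 3 and FluPRO:

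| AESI term | Criterion 3 | FluPRO |
|---|---|---|
| Diarrhea/loose stool | diarrhea | diarrhea count |
| Nausea | nausea | nausea |
| Vomiting | vomiting | vomiting count |
| Trouble breathing or wheezing | dyspnea | trouble breathing (not wheezing) |
| Abdominal cramping | none | stomach ache (loose match) |
| Pruritus, rash, hypotension, throat tightening | none | no match |

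Four of nine terms clearly overlap, and cramping is a looser fifth.

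**2. Direction of bias.** Let *d* be the drug-caused excess in the proportion with a GI event, and *c* the share of that excess recorded as AEs. If influenza-caused events are recorded alike in all arms, as blinding suggests, then approximately

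recorded difference = *c* × *d*,

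and the between-dose difference is likewise *c* × (*d* at 4000 mg − *d* at 2000 mg). Both shrink whenever *c* < 1. With assumed true rates of 17% and 5%, *d* = 12 points, and *c* = 50% gives 6 points. Halving both arms also gives 8.5% − 2.5% = 6 points, although the risk ratio then stays at 3.4.

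**3. Scale of the events.** With pretreatment at 2300 mg, GI event rates in study VIS410-102 were 16.7% (2/12) and 9.1% (1/11). In an arm of 40 that is 0.167 × 40 = 6.7 and 0.091 × 40 = 3.6 subjects. A few reclassified subjects would change the result. These were not influenza inpatients, so the rates are only a guide.

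**4. GI TEAE count (illustration only).** The documents give neither a severe GI rate for this population nor a capture share, so both are assumed. The exact binomial probability of at least 4 recorded events among 80 VIS410 recipients, one event per subject, at recorded rate *p* × *c*:

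| True severe GI rate *p* | *c* = 100% | 75% | 50% | 25% |
|---|---|---|---|---|
| 2.5% | 14% | 6% | 2% | 0.2% |
| 5% | 57% | 35% | 14% | 2% |
| 10% | 96% | 86% | 57% | 14% |

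**5. FluPRO as a backup.** Protocol 6.3.6: "Subjects who are not able to complete the baseline FluPRO Questionnaire are exempt from this assessment throughout the study". In SAP 9.2.6 a mean score of 1 or less counts as having no symptoms. The GI domain averages four items scored 0 to 4, so the top diarrhea category alone gives (4 + 0 + 0 + 0)/4 = 1.0, which counts as no symptoms. That top category is 4 or more episodes, whereas Grade 3 by stool count in the DMID table is more than 7 a day. FluPRO does not feed the AE tables and is not among the DSMB inputs named in Protocol 4.3.

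**The case against.** The strongest reply is that 9.1.3 already settles the matter. It names these events and requires EDC entry, serious or not, and a specific list normally governs a general sentence. The Amendment 1 summary of changes says the list was updated to take in single loose stools, which shows intent to capture mild events. SAP 12.1 codes all AEs without an influenza exclusion and plans an AESI table. The eCRF and Safety Plan, which may prompt sites correctly, are not in the documents reviewed.

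This defeats the stronger reading a reader might take from 9.1.2: that GI events are barred from the AE data and the signal will be missed. The documents do not support that, nor any particular fraction lost. What stands is that no sentence ranks 9.1.2 against 9.1.3, and 9.1.2 is the section headed as drawing the line between influenza symptoms and AEs.

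Other safeguards are real but partial:
- All SAEs are reported whatever the cause (9.7.1), and four treatment-related SAEs also pause dosing. This leaves severe but non-serious GI events uncovered.
- Subjects are observed during the infusion and for at least 2 hours afterwards (6.5.1). With the diphenhydramine-plus-NSAID pretreatment used here, however, the loose-stool episodes in VIS410-102 came 7 to 9, about 21 and about 22 hours after the start of infusion.
- FluPRO symptoms and GI domain scores are already compared by day and arm (Protocol 10.6.6; SAP 9.2.6), so it would be wrong to say there is no backup.
- The DSMB also sees concomitant medication and laboratory data.

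The fix also has a cost. Recording influenza-caused events raises the background rate. With an assumed independent drug effect of 16.7%, the difference is 0.167 × (1 − background): 15.9 points at 5% background and 13.4 points at 20%. Approximate power for 80 versus 40 falls from 64% to 32%. This is added noise and a modest dilution, and recording causality separately allows it to be examined.

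**Conclusion.** The point holds as an unresolved conflict between 9.1.2 and 10.7.1 on one side and 9.1.1 and 9.1.3 on the other, with possible rather than certain loss of events. The direction is clear: if drug-related events are recorded only as influenza symptoms, the VIS410-placebo and between-dose differences move toward zero. This assumes that sites treat similar events alike across blinded arms. The size is unknown, and the capture shares and severe-event rates above are assumptions.

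The effect would fall mainly on the AESI and GI rows. The any-AE proportion is less sensitive, because a subject with another AE is still counted. In VIS-C001 any-TEAE rates were 66.7% and 63.6%, although all 10 diarrhea cases were among the 30 VIS410 recipients.

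It matters because it concerns the drug's main known toxicity and a count used to protect subjects, and because unrecorded events cannot be restored later.

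**What to change.** **Protocol.** Reconcile 9.1.2, 10.7.1 and the synopsis with 9.1.1 and 9.1.3. State that an event on the AESI list that begins or worsens after the start of infusion is recorded on the AE/AESI form whatever its attribution, with causality recorded separately. Other influenza symptoms remain exempt.

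**SAP.** Beside the AESI table, show the FluPRO nausea, stomach ache, vomiting and diarrhea items by arm for the first post-infusion days, with the number of subjects who have no FluPRO data. Use item-level responses, given the domain threshold shown above.

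**Pause criterion.** The sponsor and DSMB should reconcile how events on both lists relate to the existing criterion. No change to that criterion is proposed here.

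**Cost.** One sentence with matching wording, a memo to sites and one extra table. The downside is additional non-serious AE records from influenza itself in all arms, which raise the background rate and dilute the contrast somewhat.
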